For entry into the study and randomization, all eligibility criteria MUST be met (i.e., all inclusion criteria and no exclusion criteria). Patients who meet all eligibility criteria at the Baseline Visit (day 0) will be randomized. After documentation of written informed consent and the completed screening period, clinical sites will confirm eligibility and complete randomization by accessing Almac's centralized web-based system for randomization and drug management - the Interactive Web Response System (IXRS). Additional information and instructions can be found in the MOP and appendices.

Patients will receive treatments (from among 300mg CNTX-6970 and placebo) in randomly assigned sequences. A block randomization will be used, stratifying by K-L grade to achieve balance on sequences. The randomization will be implemented by Almac's IXRS in consultation with the study statisticians. Blinding of the randomization sequence from trial subjects, staff from the Clinical Sites, CCC, and DCC will be ensured through the use of the IXRS and a designated unblinded statistician.

After Randomization, drug will be dispensed.

F.1.7. Visit 2 (Week 3)

For all visits, NEForm will be used to record the PRO scales. All other data will be directly entered into the study database or collected externally and entered into the EDC with source materials uploaded to Florence. Additional information and instructions on study activities can be found in the MOP.

1. Review remote forms completion rate with patient (confirm >80% forms completion rate or re-educate)
2. Protocol Patient Measures (PROs):
 - a) WOMAC-A (Pain Scale)
 - b) WOMAC-C (Functional Scale)

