The design for previous protocol versions included two arms, 100 mg BID CNTX-6970 and Celecoxib (as an active comparator), that have been discontinued in this version of the protocol (n=22). The total number randomized overall will therefore be n=72 (up to 77) to include the discontinued arms. These two arms were removed due to study drug supply issues and to aid recruitment feasibility. The previous protocol stipulated that the analysis of data from these arms were to be analyzed separately and thus removal of these two arms does not impact the current study objectives (except one exploratory aim in the previous protocol versions did propose examining a possible dose response between the 100 mg and 300 mg CNTX-6970 doses).

The participants in these two arms will complete the trial and will be monitored for safety events. A safety analysis for individuals in these two arms will be performed the same as for the 300 mg CNTX-6970 arm. For the efficacy objectives, exploratory analyses will be performed on the data from these two arms by computing summary statistics (e.g., means and standard deviations) comparing 100 mg CNTX-6970 to placebo (and comparing Celecoxib to placebo) for the different periods of the crossover study for the outcome measures. Formal modeling of the data from these two arms will either not be possible or will provide only limited information due to the small sample size available in these two arms. In the event that data becomes available from the biorepository samples from these two arms, that data will also be analyzed in an exploratory fashion.

■ STUDY DESIGN

D.1. Overview

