Patients will be recruited through advertisement, as well as clinician referral and self-referral. Self-referred patients will call the study sites and will be screened over the phone by the study coordinators. Those deemed potentially eligible will be scheduled for a screening visit with one of the study physicians at the sites. Based on clinical and human subject protection considerations, a potential subject will, under no circumstance, be advised to taper his/her current medication regimen prior to the screening visit.

Subjects will also be recruited through physician referral. Each site will recruit subjects via referral from primary care and specialty clinics from the communities surrounding each study site. Each site will utilize the experience of the MGH CCC to conduct outreach activities to community organizations, colleges, and other resources. Sites will regularly collaborate on strategies to recruit women and minorities, and sites will employ strategies specific to their local community, in ways that are culturally sensitive and specific to the local minority population. Retention will be enhanced with fair reimbursement (as deemed appropriate by the local IRB) for subjects' time. Site specific recruitment details are located in each site's recruitment plan.

E.2. Number of Subjects

We expect to screen approximately 300 patients to randomize up to 55 patients.

When the randomization target has been met, patients who have been screened but not yet randomized will be allowed to continue in the study unless they fail to meet randomization criteria.

E.3. Nature of Populations

Subjects must meet all of the following inclusion and none of the exclusion criteria ([Section G.4.](#)) to be eligible for participation in the study.

Protocol waivers for eligibility will not be granted under any circumstances. If, during the course of a subject's post-randomization participation in the trial, it is discovered that the subject did not meet all eligibility criteria, the justification to allow the subject to continue in the trial will be made by the PPI, with medical input from the Medical Monitor and the site's investigator(s), and will be documented in the patient's record. Whether or not the participant is allowed to remain in the trial, this will be reported as a major protocol deviation and not a waiver.

E.4. Subject Eligibility

E.4.1. Inclusion Criteria

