F.3.3.1. Automatic Pausing/Stopping Criteria for Study

If the study meets any of the following criteria at any time, the study must be stopped, and the data reviewed. These criteria will be monitored by the unblinded statistician or designee.

- a. If ≥ 2 serious adverse events (SAEs) occur in the CNTX-6970 300 mg / placebo cohort that are deemed to be possibly, probably or definitely related to the study drug, dosing will be stopped and available safety information will be reviewed to evaluate whether dosing in that arm should continue.
- b. If ≥ 2 subjects in the CNTX-6970 300 mg / placebo cohort experience Grade 3 or 4 AEs for vital signs, systemic effects, or laboratory abnormalities that are deemed to be possibly, probably or definitely related to the study drug as defined in the following guidance for industry, *Toxicity Grading Scale for Healthy Adult and Adolescent Volunteers Enrolled in Preventive Vaccine Clinical Trials*, available at, <https://www.fda.gov/media/73679/download>, dosing will be stopped and available safety information will be reviewed to evaluate whether the study should continue.

The table below should be referred to when determining severity for non-systemic effects or if an AE is not listed in the FDA guidance.

Grade	Grade Category	Intensity Definition
1	Mild	An AE that is usually transient and may require only minimal treatment or therapeutic intervention. The event does not generally interfere with usual activities of daily living.)
2	Moderate	An AE that is usually alleviated with additional specific therapeutic intervention. The event interferes with usual activities of daily living, causing discomfort but poses no significant or permanent risk of harm to the research subject
3	Severe	An AE that interrupts usual activities of daily living, or significantly affects clinical status, or may require intensive therapeutic intervention
4	Potentially Life Threatening: Emergency Room visit or hospitalization	

c. Clinical study will be terminated if any death attributable to the 300 mg CNTX-6970 treatment occurs.

F.4. Specification of Safety Parameters

F.4.1. Definition of an Adverse Event

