## 5.3 Randomization and Blinding

For entry into the study and randomization, all eligibility criteria MUST be met (i.e., all inclusion criteria and no exclusion criteria specified in the protocol). Patients who meet inclusion/exclusion criteria at the Baseline Visit (day 0) will be randomized. After documentation of written informed consent and the screening period, clinical sites will confirm eligibility and complete randomization by accessing the Almac's centralized web-based system for randomization and drug management - the Interactive Web Response System (IXRS). Subjects will be randomized equally between treatment sequences shown in Figure 1: Drug:Placebo:Placebo:Drug or Placebo:Drug:Drug:Placebo. A standard block randomization will be used, stratifying by K-L grade (stratum 1 K-L grade 1 or 2, and stratum 2 K-L grade 3 or 4) to achieve balance on randomization sequences. The randomization will be implemented by the IXRS vendor in consultation with the study statisticians. After Randomization, drug will be dispensed.

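### The by-period summaries planned for the discontinued 100 mg and celecoxib cohorts compare different patients; a per-patient active-minus-placebo difference should be added beside them

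*Protocol*

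**What the plan says.** Protocol C.4 is the only efficacy plan for the two arms dropped from the design. They hold 22 patients, who are to finish the trial. C.4 sets the total at 72, or up to 77: "The total number randomized overall will therefore be n=72 (up to 77) to include the discontinued arms". It describes the exploratory efficacy analysis as follows: "computing summary statistics (e.g., means and standard deviations) comparing 100 mg CNTX-6970 to placebo (and comparing Celecoxib to placebo) for the different periods". This applies to each outcome measure. On going further, C.4 says: "Formal modeling of the data from these two arms will either not be possible or will provide only limited information", and gives the small sample as the reason.

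C.4 specifies no interval, test or within-patient contrast for these arms. Protocol K.1 has a general rule that estimated effects are reported with 95% confidence intervals. The SAP's change history (version 4.0) records the removal of the arms, but the SAP has no analysis section for them.

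**The concern.** These patients were randomised in a crossover and are to complete it, so each can serve as his or her own control. Within one period, the patients on active and those on placebo are different people. A by-period table of means and SDs therefore carries the full between-patient variance, and the within-patient SD cannot be recovered from it. Protocol D.1 justifies the design by the gain from repeated exposure within each subject, putting power at 0.20-0.25 for a parallel design and 0.9-1.0 for the crossover. C.4 sets that gain aside where the sample is smallest.

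The reason given covers model fitting only. A difference per patient is itself a summary statistic and cannot fail to converge.

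Within these documents, the 100 mg cohort is the only placebo-controlled evidence on that dose in knee osteoarthritis, since the Phase 1 studies were in healthy volunteers. Celecoxib was the active comparator. Both cohorts are exploratory, but they are small enough that the choice of summary decides whether anything can be read from them.

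**Working it through.** **Inputs**

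- Patients: 22 over both arms (C.4). The split is not given; I assume 11 per cohort and show 7 to 15.
- Layout: two active and two placebo periods per patient, half the cohort on active in any period. SAP 5.3 gives "Drug:Placebo:Placebo:Drug or Placebo:Drug:Drug:Placebo" with equal allocation for the current cohort. I assume the same for the discontinued arms.
- Between/within variance ratio R: 2 and 5 were simulated and 7 is cited (Protocol K.4, SAP 6).
- Dropout: 15% per period (K.4).
- Scale: total SD 1, one value per period, within-patient variance w = 1/(1+R), no patient-by-treatment variation.

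**The plan's own figures.** 50 + 22 = 72 and 55 + 22 = 77, as in C.4. Completers: 50 × 0.85^4 = 26.1 (stated 26) and 55 × 0.85^4 = 28.7 (stated 29). C.4 gives no precision figure to reproduce. As a check on the variance formula, power at d = 0.35 from Φ(0.35/√(w/n) − 1.96) is 0.99 (n=50, R=2), 0.87 (n=26, R=2) and 0.99 (n=26, R=5). K.4 reports about 0.95, 0.81 and 0.96 by simulation. The closed form is somewhat optimistic. Multiplying the variance by 1.25 (my assumption) gives 0.97, 0.79 and 0.97; paired half-widths would then be √1.25 = 1.12 times those below.

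**Step 1: one period, active versus placebo, 5 against 6 patients.** SE = √(1/5 + 1/6) = 0.61. With t on 9 df (2.262), the half-width is 1.37 SD. Power at d = 0.35 is about 8%.

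**Step 2: per-patient mean of two active periods minus mean of two placebo periods.** The variance per patient is w/2 + w/2 = w, so SE = √(w/n).

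| | R = 2 | R = 5 |
|---|---|---|
| w | 0.333 | 0.167 |
| SE, n = 11 | 0.17 | 0.12 |
| Half-width, 10 df | 0.39 | 0.27 |
| Half-width, averaged over sequences, 9 df | 0.40 | 0.28 |
| Power at d = 0.35 | 44% | 73% |

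For n = 7 to 15 the single-period half-width runs from 1.96 to 1.12. The paired half-width runs from 0.53 to 0.32 (R=2) or 0.38 to 0.23 (R=5).

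**Step 3: where the factor comes from.** The SE ratio of step 1 to step 2 is √(4(R+1)), taking equal halves: 3.46 at R=2, 4.90 at R=5 and 5.66 at R=7. It has two parts:

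- Treating all active-period and all placebo-period values as unpaired, rather than paired, costs √(R+1) = 1.73 to 2.45.
- Using one period instead of four costs a further factor of 2.

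**Step 4: what reduces the gain.**

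- Dropout: 11 × 0.85^2 = 7.9 patients finish block 1 and 11 × 0.85^4 = 5.7 finish all four periods. With 8 patients and block 1 only, the paired SE is √(2w/8) = 0.289 or 0.204. On 6 df (t = 2.447) the half-width is 0.71 (R=2) or 0.50 (R=5). The single-period figure is √(1/4 + 1/4) × 2.447 = 1.73. The ratio is 2.45 to 3.46.
- Patient-by-treatment variation: if it adds variance equal to w to each patient's difference, the full ratio falls to √(2(R+1)) = 2.45 to 3.46.

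**Step 5: what the by-period table does keep.** With complete data in this layout, the simple average of the four period differences equals the average of the two sequence means of the per-patient difference. The point estimate can therefore be recovered from the table; its within-patient standard error cannot.

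**Cross-check with D.1.** Power of 0.9 against 0.20-0.25 implies an SE ratio of (1.28 + 1.96)/(−0.84 + 1.96) = 2.9 to (1.28 + 1.96)/(−0.67 + 1.96) = 2.5, which agrees in direction.

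**The case against.** The strongest reply is that C.4 promises very little. It plans exploratory summaries, names means and SDs only as examples, and specifies no interval for these arms. It does not forbid a paired summary, and its reference to the different periods could mean active periods pooled against placebo periods. All of this stands. A reader might infer that the plan prescribes intervals 3.5 to 5 times too wide because pairing is thrown away. The documents do not support that: no interval is planned, and the figure mixes lost pairing with one period set against four.

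A reader might also want the sentence saying that modelling "will either not be possible or will provide only limited information due to the small sample size" removed. It should stay. It concerns formal modelling, and the paired half-width at R=2 (0.39 SD) still exceeds the planned effect of 0.35. Nor do the documents state that between-patient variance is at least twice within-patient variance. They call it generally larger and simulate ratios of 2 and 5.

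Two further limits stand. The sequences and the split of the 22 belong to superseded versions and are not given. The justification for a four-week washout rests on PK/PD data for CNTX-6970 only, with nothing comparable for celecoxib.

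What the reply does not answer is why the one summary suited to a crossover is left unstated when it needs no model.

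**Conclusion.** The point holds as a gap in the exploratory plan that is cheap to close. Read literally, C.4 gives between-patient comparisons only, and sample size is no reason to omit the within-patient one. Under the stated assumptions (11 per cohort, two active and two placebo periods, complete data, no patient-by-treatment variation, R of 2 to 5), any single-period 95% interval would have a half-width near 1.37 SD. The four-period within-patient difference gives about 0.39 or 0.27. Of that gap, a factor of about 1.7 to 2.4 is due to pairing; the rest is the number of periods used. Dropout or patient-by-treatment variation narrows it, but in each case worked above the paired summary remains the more precise.

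It would go too far to call the by-period data unreadable, because the point estimate is recoverable, or to call the paired estimate precise. The primary 300 mg comparison is not affected.

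**What to change.** Add one paragraph to C.4 or the SAP, labelled exploratory, and keep the by-period table beside it:

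- For each discontinued cohort, compute per patient the mean last-2-week WOMAC-A in active periods minus the mean in placebo periods, for patients with at least one complete block. Do the same for other outcomes measured in every period.
- Average over the two sequences and report the mean, SD and a t-based 95% interval on n − 2 df.
- Show one-block and two-block patients separately, or weight them, since their differences have variance 2w and w.
- State the split of the 22 patients and the sequences used in the earlier protocol versions.
- Keep the caveat about limited information.
- State that the estimate assumes no carryover into weeks 5-6, and that for celecoxib the documents give no PK/PD support for this.

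The cost is a paragraph and a few lines of code, with no new data. Fixing the summary in advance also avoids a later choice between paired and unpaired results.
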